6.13.7. Echocardiograms/Doppler

Echocardiograms assessment of normality and clinical significance will be listed by treatment arm. Results of echocardiograms, including LV dimension, LA volume, LV mass, left ventricular ejection fraction (LVEF), valvular regurgitation and wall motion will also be provided in patient listings. Absolute or percent change from baseline for quantitative variables will be included. Shift tables on maximum change from baseline severity will be provided for each valvular regurgitation. Graphical representation of LVEF may be provided if necessary.

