Efficacy: The primary analysis is to compare the HR between LY2157299 monohydrate plus lomustine therapy with lomustine plus placebo therapy based on OS using a Bayesian OS model which augments current control data with additional information from historical data. The same Bayesian OS model will be used to estimate the HR between LY2157299 monohydrate monotherapy and lomustine plus placebo therapy. Hazard rates and ratios of and between the 3 treatment arms will also be estimated for PFS. Response rates based on the RANO criteria will be estimated.

Safety: Summary statistics, plots, and listings for all safety data will be provided. Summaries of both acute toxicity (occurring in the first 3 cycles) and chronic toxicity will be provided by treatment arm.

Health Outcomes: Neurocognitive function will be compared to population norms, summarized for each assessment period, and change over time will be explored. Time-to-neurocognitive progression will be assessed between arms. Data from the MDASI-BT will be summarized for each assessment period. This summary will include descriptive statistics and change from baseline (including time to worsening of symptoms). The MDASI-BT will be reported as core symptoms, brain tumor symptoms, symptom interference, and symptom groupings.

Pharmacokinetic (PK): Exposure of LY2157299 monohydrate using population PK analysis will be compared. This analysis will explore the impact of covariates, such as demographic factors, on the relevant PK parameters. Exploratory PK/PD analyses may be conducted to identify the exposure-biomarker response (such as S100 β and LDH) relationship.

Pharmacodynamic (PD): Tumor tissue for pSMAD, MGMT promoter status, and serum assessments for S100 β , LDH, and T regulatory cells will be collected and correlated with clinical benefit.

Translational Medicine: Previously described genetic profile signatures will be studied for their relevance to the clinical outcome of LY2157299 monohydrate monotherapy or LY2157299 monohydrate plus lomustine and to the clinical outcome of recurrent malignant glioma.

3. Table of Contents

A Phase 2 Study of LY2157299 Monohydrate Monotherapy or LY2157299 Monohydrate plus Lomustine Therapy compared to Lomustine Monotherapy in Patients with Recurrent Glioblastoma

Section	Page

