12.2.10. Safety Analyses

All safety summaries and analyses will be based upon the safety population as defined in Section 12.2.1.

Overall exposure to study drug, the numbers of patients completing each cycle, and the dose intensity will be summarized using descriptive statistics. The number of patients with any dose adjustment will be presented for entire treatment period as well as for each cycle. The number of patients with dose reductions, dose delays, or dose omissions will also be summarized, as will the reasons for dose adjustments.

Common Terminology Criteria for Adverse Events (CTCAE) version 4 will be used to report AEs. The MedDRA Version 14.0 (or higher) will be used when reporting AEs by MedDRA terms. The MedDRA lower level term (LLT) will be used in the treatment-emergent computation.

A TEAE is defined as an event that first occurred or worsened in severity after baseline, based on the MedDRA LLT and CTCAE severity grade. This means that any episode of the same AE with the same grade as at baseline that starts after the first dose of study treatment will not be defined as treatment emergent, even if now considered possibly drug related.

An overall summary of AEs will be provided for AEs deemed by the investigator to be possibly related to study medication, and repeated for events regardless of study drug causality. Incidence rates of these events will be compared between treatment arms using Fisher's exact test. These analyses and summaries will be repeated for TEAEs.

The TEAEs will be summarized separately for both MedDRA and CTCAE dictionaries, by their respective System Organ Class (SOC) terms and by decreasing frequency of their respective preferred term (PT) within SOC.

The number of evaluable patients who experienced a TEAE, SAE, AE related to study drug, died, or discontinued from the study due to an AE will be summarized by treatment.

The CTCAEs, separated by those defined as laboratory and non-laboratory CTCAEs, will be summarized by CTCAE term and maximum CTCAE grade, including the total for maximum Grade 3 and 4. These summaries will be provided for events regardless of study drug causality,

and repeated for events deemed by the investigator to be possibly related to study medication. These summaries will be repeated for TEAEs.

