A calculated CTCAE grade will be provided for all laboratory results which can be used independently of clinical judgment to determine a CTCAE severity grade. These will be summarized by CTCAE grade in a separate table, linking the CTCAE term to the laboratory term in question.

Reasons for death will be summarized separately for on-therapy, within 30 days of last dose of study drug and during the long-term follow-up periods. The SAEs will be summarized by MedDRA and CTCAE PT.

Hospitalizations and transfusions during the study treatment period or during the 30-day postdiscontinuation follow-up period will be summarized by treatment group.

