12.2.10.1. Cardiac Safety Analyses

Refer to [Attachment 1](#) and [Attachment 2](#) for timing of ECGs, ECG chemistry, and ECHOs.

Echocardiography/Doppler assessments will be done as outlined in [Attachment 6](#).

Baseline ECGs are ECGs performed either during screening or predose during the study. Changes in QT from baseline, delta QT, will be calculated by subtracting the respective reading taken at the same nominal time during screening from the reading taken after LY2157299 dosing on specified days in [Attachment 1](#). Similarly, changes in RR from baseline, delta RR, will be calculated. Delta QT will then be analyzed using a linear mixed-effects model (Dmitrienko and Smith 2003).

In addition, listings and summaries of outlying corrected QT intervals (QTc [QTc – Bazett's correction (QTcB) and QTc – Fridericia's correction (QTcF)]) will be provided for each scheduled time point.

If data warrant, additional exploratory analyses may be conducted using appropriate modeling techniques.

The ECG chemistry laboratory values will be listed and summarized separately from other laboratory values.

Individual patient listings and summaries by treatment arm will be provided for all echocardiograph variables. Shift tables indicating maximum changes from baseline will be provided for qualitative variables and absolute and/or percent change from baseline for quantitative variables.

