6.13.2. Adverse Events

The Common Terminology Criteria for Adverse Events (CTCAE) version 4 will be used to report adverse events in CTCAE terms. The current MedDRA Version 14.0 (or higher) at the time of reporting will be used when reporting adverse events by MedDRA terms. The MedDRA Lower Level Term (LLT) will be used in the treatment-emergent computation.

Treatment-emergent adverse events (TEAE) are defined as follows:

- Any event that first occurred or worsened in severity after baseline, based on the MedDRA LLT term and CTCAE severity grade. This means that any episode of the same AE with the same grade as at baseline that starts after the first dose of study treatment will not be defined as treatment emergent, even if now considered possibly drug related.
- Or any PEC (emerged prior to informed consent) or any AE (emerged after signed informed consent) that were still present prior to first dose but has increased in severity (CTCAE grade) following the start of treatment, regardless of causation.

A listing of all adverse events by patient, including pre-existing conditions, will be presented. This listing will include patient number, adverse event (actual term, CTCAE term, and preferred term), event start and end dates, CTCAE grade, relationship to study drug/procedure, seriousness, and outcome. A listing of SAE will be produced using the similar format.

An overall summary will be provided for possibly drug-related AEs. The number and percent of evaluable patients will be summarized by treatment for each category below.

- Patients with at least one AE
- Patients with at least one TEAE
- Patients with at least one grade 3 or 4 AE
- Patients with at least one SAE
- Patients who discontinued due to AE
- Patients who discontinued due to SAE
- Patients who died on therapy
- Patients who died within 30 days of last dose of study drug (LY2157299/placebo or lomustine)

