6.13.5. Vital Signs and Other Physical Findings

Vital signs measurements including height, weight, respiratory rate, temperature, blood pressure and post-baseline ECOG performance status will be listed by treatment arm.

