6.13.9. Hospitalizations and Blood Transfusions

Patients who were hospitalized due to SAE will be included in the AE listings.

Patients that received blood transfusions, including the blood products received (that is packed red blood cells, platelets, fresh frozen plasma, or whole blood) during the study treatment period or during the 30-day postdiscontinuation follow-up period will also be listed.

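### SAP 6.13 leaves out, without giving a reason, by-arm safety summaries that the protocol promises: most echocardiography results, hospitalizations and transfusions, the all-cause AE overview, and the acute/chronic split

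*SAP*

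**What the plan says.** **Echocardiography.** Protocol 12.2.10.1: "Individual patient listings and summaries by treatment arm will be provided for all echocardiograph variables". The same paragraph adds shift tables for qualitative variables and change from baseline for quantitative ones. SAP 6.13.7 states that "left ventricular ejection fraction (LVEF), valvular regurgitation and wall motion will also be provided in patient listings", and the same sentence covers LV dimension, LA volume and LV mass. The section then says that change from baseline will be included for quantitative variables, provides shift tables for valvular regurgitation, and makes an LVEF graph optional.

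**Hospitalizations and transfusions.** Protocol 12.2.10: "Hospitalizations and transfusions during the study treatment period or during the 30-day postdiscontinuation follow-up period will be summarized by treatment group". SAP 6.13.9: "Patients who were hospitalized due to SAE will be included in the AE listings". Transfused patients are likewise listed.

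**AE overview.** Protocol 12.2.10 asks for an overall AE summary for events judged possibly related, "and repeated for events regardless of study drug causality. Incidence rates of these events will be compared between treatment arms". SAP 6.13.2: "An overall summary will be provided for possibly drug-related AEs". Eight patient-count rows follow, including grade 3 or 4 AEs, SAEs, discontinuations and deaths.

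**Acute and chronic toxicity.** Protocol synopsis, Statistical Methods: "Summaries of both acute toxicity (occurring in the first 3 cycles) and chronic toxicity will be provided by treatment arm". SAP 6.13 contains nothing that corresponds to this.

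**The concern.** Protocol 5.6.3 names the heart and great vessels as major target organs of toxicity. Attachment 6 explains that serial echocardiograms are done to establish cardiac safety and that quantitative measurement is the aim. Protocol 10.3.2.2 adds a central reading for the study report. Safety relative to lomustine plus placebo is a secondary objective in both documents.

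A patient listing gives no by-arm mean, change or proportion. Under SAP section 3 a contractor produces the pre-planned tables, so a table that the SAP does not name may not be made, or may be designed only after the data have been seen. An overview limited to related events also rests on investigator attribution, and that attribution is open-label in the monotherapy arm.

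**Working it through.** No formula applies. The check sets the two documents side by side.

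1. **Does the SAP distinguish listing from summarizing?** Yes. SAP 6.13.8 (pulmonary function) and the ECG chemistry sentence in SAP 6.13.6 call for both. SAP 6.13.7 does not call for summaries of the ECHO measurements, and SAP 6.13.9 does not call for summaries at all.

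2. **ECHO count.** SAP 6.13.7 names six result types: LV dimension, LA volume, LV mass, LVEF, valvular regurgitation and wall motion. One of them, regurgitation, has a table, and the sentence providing it does not say that it is by arm. That leaves 6 − 1 = 5 without a named table: four quantitative measures and wall motion. The sentence on change from baseline directly follows the listing sentence and names no statistic, visit or arm.

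3. **Does general text fill the gap?** SAP 6.13 promises counts and percentages in each arm, which would not describe a change in LVEF, volume or mass. SAP 6.1 promises descriptive statistics by arm, with mean, median and SD for continuous variables. That could be read as covering ECHO, but the specific section assigns these results to listings, so the general text does not clearly override it.

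4. **Hospitalizations and transfusions.** The change is from a by-group summary to a listing. The SAP also narrows hospitalizations to those due to an SAE, and Protocol 12.2.10 has no such limit.

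5. **AE overview.** Besides the repeat regardless of causality, Protocol 12.2.10 separately calls for by-treatment counts of patients with a TEAE, an SAE, a related AE, death, or discontinuation due to an AE. It does not restrict that set to related events. The only SAP table with this layout is introduced as related-only.

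6. **Acute/chronic split.** It appears only in the protocol synopsis. Protocol 12.2.10 does not repeat it and the SAP omits it.

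7. **Is there an explanation?** The SAP is based on the protocol approved on 10 November 2011, and the protocol supplied is amendment (a). The amendment summary in Attachment 11 shows no change to 12.2.10, so the version gap does not account for the differences. SAP 6.1 says that departures will be justified in the SAP and/or the study report. The safety sections of the SAP offer no justification.

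8. **What the SAP keeps.** SAP 6.13.2 has AE and TEAE tables regardless of causality with Fisher's exact tests between arms, all-cause SAE tables, and all-cause maximum-grade tables. SAP 6.13.3 summarizes reasons for death, and SAP 6.6 summarizes discontinuations by reason and arm. SAP 6.13.6 models change in QT with between-arm differences and 90% CIs. SAP 6.13.7 keeps the regurgitation shift tables.

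**The case against.** A reader might infer that cardiac and overall toxicity cannot be compared between arms. The documents do not support that. The tables and tests in step 8 allow an all-cause comparison of AEs, SAEs and severity, and a modelled comparison of QT. Valvulopathy, a named nonclinical lesion, keeps its regurgitation shift tables. Clinically significant findings that lead to a diagnosis are reportable under Protocol 10.3.1, and inpatient hospitalization is an SAE criterion, so such events reach the all-cause tables when recorded. The related-only limit affects one overview table and not the SAP's AE reporting as a whole.

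It is also fair to say that SAP 6.13.7 is under-specified and does not forbid summaries, given the general promise in SAP 6.1, and that a justification could still appear in the study report. The acute/chronic split has thin support, since it stands only in the synopsis.

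Vital signs might be added to the list, because SAP 6.13.5 says "Vital signs measurements including height, weight, respiratory rate, temperature, blood pressure and post-baseline ECOG performance status will be listed by treatment arm" and does not name heart rate. That is mostly preference. The wording is not exhaustive, Protocol 12.2.10 specifies no vital-sign table, and change in RR interval is calculated and enters the QT model.

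These points limit the consequence. They do not supply an explicit by-arm summary of LVEF, chamber measures and wall motion, of hospitalization and transfusion burden, or of the all-cause overview totals. SAE tables by preferred term do not count hospitalized patients.

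**Conclusion.** The point holds as a set of unjustified gaps between the protocol and the SAP, and it should be fixed. Four commitments are affected. For ECHO, five of the six named result types lack an explicit by-arm table. Hospitalizations and transfusions are listed only. The AE overview lacks its all-cause version. The acute/chronic summaries are omitted outright. The ECHO gap matters most, because it concerns the named target organ and a secondary objective.

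The conclusion rests on reading the specific listing-only and related-only sentences as governing over the general text in SAP 6.1 and 6.13. It does not extend to a claim that toxicity cannot be compared between arms. No loss of precision is quantified: the documents give no SD for change in LVEF, and the arm sizes are redacted.

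**What to change.** - **SAP 6.13.7:** add by-arm descriptive statistics and change from baseline for each quantitative ECHO variable, and by-arm shift tables for all qualitative variables, including wall motion.
- **SAP 6.13.9:** add counts and percentages by arm for hospitalizations and for transfusions, over the treatment period and the 30-day follow-up.
- **SAP 6.13.2:** produce the overview for related events and again regardless of causality, and split the AE tables into Cycles 1 to 3 and later cycles.
- **Optional, SAP 6.13.5:** summarize change in heart rate and blood pressure by arm.

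Where the sponsor prefers to leave a table out, the SAP should state why. The cost is a few extra tables, with no new data collection.

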6.13.8. Pulmonary Function Tests

Pulmonary function tests (PFT) will be performed at baseline and approximately every 6 months for those patients receiving lomustine. Changes from baseline for PFT variables (FEV1, FVC, FEV1/FVC ratio, DLCO) will be listed and summarized by treatment arm.

6.13.9. Hospitalizations and Blood Transfusions

Patients who were hospitalized due to SAE will be included in the AE listings.

Patients that received blood transfusions, including the blood products received (that is packed red blood cells, platelets, fresh frozen plasma, or whole blood) during the study treatment period or during the 30-day postdiscontinuation follow-up period will also be listed.

6.14. Subgroup Analyses

Subgroup analyses on health outcome measures are described in [Section 6.11](#). In addition, exploratory analyses may be performed to generate hypotheses about the efficacy of study therapy in certain subgroups to be tested in future clinical trials.

6.15. Protocol Violations

Protocol violations will be identified based on information recorded on the investigator log and through statistical programming of the data. A list of data dependent protocol violations in general and specific to this study is as follows:

General:

- Not meeting protocol inclusion/exclusion criteria [2], [3], [5] to [9], [11], [13] to [17]
- If patient with “entry criteria not met” is marked at screening (visit 0) but patient moves on to cycle 1
- Use of prohibited concomitant therapy (See Protocol Section 9.7):
 - Chemotherapy;
 - Radiation therapy;
 - Immunotherapy;
 - Cancer-related hormonal therapy;
 - Surgery for cancer;
 - Experimental/investigational medication;

- Routine use of granulocyte colony-stimulating factors. They may be used for patients who have ANC $\leq 0.5 \times 10^9/L$, neutropenic fever, or documented infections at investigator's discretion, but cannot be used during Visit 0 to meet hematological inclusion criteria and must be discontinued at least 24 hours prior to the start of therapy.
- Any disease progression requiring other forms of specific anti-tumor therapy will be cause for early discontinuation from the study.
- Treatment compliance with LY2157299 is less than **CCI**% of the prescribed/intended amount of drug per cycle
- Incorrect dose administered (e.g., more than intended)
- Informed consent violations, including patients that have had cerebral spinal fluid (CSF) collected but informed consent for CSF not signed

Study specific:

- Visit outside visit intervals specified in protocol:
 - lomustine therapy is held for ≥ 12 weeks from the last dose of lomustine due to any reason and the patient is not discontinued from the study
- If the patient had two prior dose reductions in lomustine therapy and needs a third reduction due to toxicities but is not discontinued from lomustine therapy
- Failure to perform PK collections
 - only collections "not done" are considered significant protocol violations.
- Failure to collect samples of tumor tissue (at screening only)
- Failure to perform safety procedures or missing safety measurements per requirements in Study Schedule (Attachment 1 in Protocol)
 - Hematology/chemistry
 - ECG
 - ECHO

Note: only collections "not done" are considered significant protocol violations.

This list of these protocol violations may be included in a patient listing, and patients with missing safety assessments will be identified from a tabular display of individual patient assessment according to study schedule. These data dependent protocol violations, together with the data from the investigator log will be summarized to include only important protocol violations for the final study report.

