Patients and investigators will be blinded to the administration of LY2157299 using a LY2157299-matched placebo. In contrast to the favorable toxicity profile of LY2157299, blinding of lomustine is difficult to ensure due to its well-characterized bone marrow toxicity. Given the other toxicity concerns, a blinding of lomustine is not warranted for this study.

If a patient can no longer tolerate lomustine therapy but the patient is benefitting from the treatment, the patient may continue LY2157299 or placebo treatment after approval by the Lilly Clinical Research Physician (CRP). Treatment may continue until disease progression or additional unacceptable toxicity occurs (see Section 9.4.1).

After the trial is completed, biomarker assessment of the tumor tissue will be used to determine whether treatment with LY2157299 had a particular impact on subtypes with a gene expression profile associated with TGF- β -associated signaling. This retrospective evaluation will help to identify a possible subgroup of patients that may respond to LY2157299 treatment, either alone or in combination with lomustine. Hence, the collection of tumor tissue is important to design future Phase 3 studies or to enrich potential responders in future GB studies. Because PK may be associated with toxicity, sparse population PK sampling is being implemented in this study. Finally, the health outcome measures are important for evaluating patient reported outcomes and are needed for future Phase 3 study designs.

9. Treatment

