9.4.1.1. Lomustine Hematologic Adverse Events

Blood counts should be monitored weekly and repeat doses of lomustine should be given every 6 weeks due to possible delayed hematotoxicity. Dose adjustments at the start of a subsequent cycle of therapy will be based on the lowest platelet and ANC (nadir) counts. A repeat dose of lomustine should not be given until ANC and platelet counts return to baseline levels or Grade 1, which usually occurs within 6 weeks.

Any patient who requires a dose reduction due to hematologic AEs will continue to receive a reduced dose for the remainder of the study. Any patient with 2 prior dose reductions, who experiences a toxicity that would cause a third dose reduction, must be discontinued from

lomustine therapy. A patient who, for any reason, cannot be administered lomustine for 12 weeks from the last lomustine dose, must be discontinued from *lomustine therapy*.

If either of the foregoing occur and, in the judgment of the treating physician, it is felt that the patient is benefiting from the treatment and after approval by the Lilly CRP, the patient may continue LY2157299 or placebo treatment, until disease progression or additional unacceptable toxicity occurs.

Treating physicians at the investigative sites will dose adjust lomustine based upon the following suggested guidelines (refer to [Table JBAL.9.1](#)) or best institutional practices:

Table JBAL.9.1. Dose Adjustment Guide for Lomustine Based on Nadir Hematologic Values for Preceding Cycle

Nadir After Prior Dose		Percentage of Prior Dose to be Given
ANC ($\times 10^9/L$)	Platelets ($\times 10^9/L$)	
LLN – 1.5	>75	100%
1.5 – 1.0	25 – 75	70%
<1.0	<25	50%

Abbreviations: ANC = absolute neutrophil count; LLN = lower limit of normal.

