6.10.4. Sensitivity Analyses

Additional analyses may be carried out to judge the influence of any patients who did not meet enrollment criteria but were inadvertently enrolled and continued on treatment after obtaining approval from the sponsor and/or patients who have continued treatment after objective disease progression. A subanalysis will be conducted by excluding such patients to determine their influence on the final study results.

Additional sensitivity analyses may also include the use of different censoring dates in the time-to-event analyses.

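### SAP 6.15's 12-week lomustine violation rule requires leaving the study, while Protocol 9.4.1.1 requires stopping lomustine only, so protocol-compliant patients can be listed as violators

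*SAP*

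**What the plan says.** Protocol 9.4.1.1 gives two triggers for stopping lomustine: a toxicity that would need a third dose reduction, and 12 weeks without a dose. On the second it says: "A patient who, for any reason, cannot be administered lomustine for 12 weeks from the last lomustine dose, must be discontinued from", and the object of that sentence is lomustine therapy, not the study. The next paragraph covers both triggers ("If either of the foregoing occur and, in the judgment of the treating physician") and states what may follow when the physician sees benefit: "after approval by the Lilly CRP, the patient may continue LY2157299 or placebo treatment, until disease progression or additional unacceptable toxicity occurs". Protocol 8.2 gives the same permission to patients who can no longer tolerate lomustine.

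SAP 6.15 has one bullet for each trigger. The third-reduction bullet describes a patient who "needs a third reduction due to toxicities but is not discontinued from lomustine therapy", which matches the protocol. The 12-week bullet describes a hold of that length "from the last dose of lomustine due to any reason and the patient is not discontinued from the study", which does not. On method, the section opens: "Protocol violations will be identified based on information recorded on the investigator log and through statistical programming of the data".

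**The concern.** The protocol prescribes one action for both triggers. The SAP prescribes two, and the one for the 12-week trigger is stricter than the protocol. Because violations are found partly by program, the wording of the bullet is likely to become code. A site that did what Protocol 9.4.1.1 allows could then appear in the violation listing beside a site that restarted lomustine after the limit, with nothing in the flag to separate them. This would happen only in the two lomustine arms, which are the arms of the primary comparison. What is at stake is the accuracy of the record of protocol conduct in those arms. No efficacy estimate is at stake.

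**Working it through.** There is no stated figure to reproduce. The check sets the two rules side by side and runs each possible course after a lomustine gap through them.

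**Inputs**
- Required action after 12 weeks: stop lomustine (Protocol 9.4.1.1).
- Permitted continuation: LY2157299 or placebo, with judged benefit and sponsor physician approval (Protocol 9.4.1.1 and 8.2; Protocol 9.5 after the six planned doses).
- Stopping treatment is not leaving the study: survival is collected on everyone, including after study drug ends (Protocol 8.1), and SAP 6.6 reports discontinuation from treatment and from the study as two separate statuses.
- Violation rule: SAP 6.15, 12-week bullet.

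**Cases**

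| Course of the patient | Protocol 9.4.1.1 | SAP rule, literal | SAP rule, *the study* read as study treatment | Rule keyed to lomustine therapy |
|---|---|---|---|---|
| A. Held to 12 weeks, lomustine stopped, blinded drug continued with approval | Compliant | Flag | Flag | No flag |
| B. As A, but without approval | Lomustine rule met, approval condition broken | Flag | Flag | No flag from this bullet; needs its own item |
| C. Held 12 weeks or more, then lomustine resumed | Violation | Flag | Flag | Flag |
| D. Held to 12 weeks, all study drug stopped, alive in OS follow-up | Compliant | Flag | No flag | No flag |
| E. Lomustine permanently stopped before 12 weeks, blinded drug continued with approval | Compliant | Flag only if a hold is coded as time since last dose | Same as literal | No flag |

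Case A is flagged on either reading of *the study*, because the patient is in the study and still on study treatment. Case D is flagged only on the literal reading. Case E turns on how a hold is coded. Flagging B and C is right, but the present bullet gives them the same label as A.

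**Timing**
- 12 weeks = 12 × 7 = 84 days, and two dosing intervals = 2 × 42 = 84 days.
- The first lomustine dose is on Day 7, so the rule can first apply on Day 7 + 84 = Day 91. With the Day 7 ± 2 window of the Study Schedule, that is Day 5 + 84 = 89 to Day 9 + 84 = 93.

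**How often**
The documents give no rate of 12-week gaps and none of approved continuation, so no count can be computed. Table JBAL.5.1 in the protocol gives some context. Median PFS in its two lomustine control arms is 1.64 months (1.64 × 30.4 ≈ 50 days) and 82 days. Both fall before Day 91. Treatment ends at progression. If patients in this trial progress at a similar pace, at least half would be past the point of case A before the rule could first apply. Case A also needs a full 12-week gap, judged benefit and approval.

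**Version check**
SAP section 3 says the SAP follows the protocol approved on 10 November 2011. The change list for amendment (a) shows no change to 9.4.1.1, and no blacked-out text falls in either rule, so neither explains the mismatch.

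**The case against.** The best defence is the word *held*. In ordinary use a held drug is paused with a view to resuming, and a drug that has been stopped is no longer held. On that reading the bullet looks for patients whose lomustine is still nominally running past 12 weeks, and a patient formally taken off it is not a target. This has force for case E, and it is why the reach to patients stopped earlier is left open here. It does not rescue case A, where lomustine was on hold for the full 12 weeks before it was stopped and the patient stayed in the study.

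A second defence is loose drafting. Protocol 9.7 says that progression needing other therapy ends participation in the study, yet such patients are followed for survival. So *the study* may mean study treatment, and a strictly literal rule would sweep in so many patients in follow-up that a programmer would notice. That is a fair reason not to rely on case D. It leaves case A unchanged.

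Third, the consequences are slight. The investigator log is a second source, approved continuations are known to the sponsor by definition, the listing is optional, and the study report summarizes only violations judged important. All of this stands, and it sets the size of the point.

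A reader might infer more: that the flag removes compliant patients from an analysis. The documents do not support that. SAP 6.10.4 names its exclusion groups as "patients who did not meet enrollment criteria but were inadvertently enrolled and continued on treatment after obtaining approval from the sponsor" and patients treated beyond objective progression, and a 12-week lomustine hold is neither. SAP 6.1.1 plans a safety subanalysis without patients who should have been discontinued, and does not define them there. SAP 6.5 uses the same description for patients who failed entry criteria, and nothing ties it to this bullet.

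**Conclusion.** The mismatch is real and the rule is wrong as written. It contradicts Protocol 9.4.1.1 and its own neighbouring bullet, and on either reading of *the study* it classes an approved, compliant continuation after a 12-week hold as a violation. The point is minor. It touches the violation listing and, if the item passes the importance filter, the violation summary. The primary OS analysis and its decision rule do not depend on it.

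The number affected is unknown. It could be zero, and at most it is every approved continuation after such a gap plus, on the literal reading, every patient in case D. The judgement that it is small assumes progression roughly as fast as in the two lomustine arms of Table JBAL.5.1, and a program that does not treat every patient off lomustine for 12 weeks as held. A reader might go further and conclude that most patients who come off lomustine would be listed as violators. That would need both the literal sense of *the study* and a hold coded as time since last dose, and the SAP commits to neither.

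**What to change.** In the 12-week bullet of SAP 6.15, replace the condition on discontinuation from the study with one on discontinuation from lomustine therapy, as in the next bullet and in Protocol 9.4.1.1. Add a separate item for LY2157299 or placebo continued after lomustine was stopped under 9.4.1.1 without sponsor physician approval, so that this breach is still caught. Every true breach of the lomustine-stopping rule remains flagged. The cost is one edited line and one added line in the SAP, with the matching change to the program; the added item needs the approval to be available to the program or the log.
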